**PURPOSE OF STUDY AND BACKGROUND**

**Purpose of the Study:** To assess the effectiveness of upper extremity prosthesis in improving the upper extremity function of children with cerebral palsy who have limited use of their hands

**Background**

Cerebral palsy is the most common childhood disability, affecting approximately two to three out of every one thousand live births in the United States, and the most common form is spastic (77%) (CDC). Up to 83% of children with cerebral palsy have upper extremity involvement, which limits their ability to live and work independently.

In the past, there have been very few well-designed studies proving efficacy of various treatment modalities of the upper extremity in patients with cerebral palsy. Traditional methods such as surgery have only weakly positive data. In two recent comprehensive reviews, the most supportive data was found for therapeutic techniques, in particular, constraint-induced movement therapy (CIMT) and bimanual training. A review of over 100 patients studied since 1997 showed that forced use of the weaker hand and intensive bimanual training in patients with unilateral spastic cerebral palsy can improve measures of dexterity and use. Additional focuses include other intensive and structured therapies, Botox injections, and family-centered or home programs. However, most treatments are effective only in patients with relatively advanced ability.

The Manual Ability Classification System (MACS) is a simple way to describe how children with cerebral palsy use their hands during routine activities at school and home. Level I indicates a child who has full use, while level V would be one without any use. The intervening levels describe increasingly severe limitations; level II pertains to a child who can handle most objects, level III to someone who handles items with difficulty, and level IV to a patient who can only use their hands in adapted situations. Many of the intensive and structured therapeutic regimens were developed for children at higher functioning MACS levels. For children with lower levels of activity, MACS IV and V, there are much fewer available treatments.

Upper extremity function in cerebral palsy patients can have a profound effect on their quality of life and ability for self-care. Children with MACS IV or V comprise 15-30% of the pediatric cerebral palsy population and are more globally involved. Although they are a minority of total patients, they consume a large portion of resources for care, and should have options for improvement of the upper extremity.

In recent years, three-dimensional printing has expanded to medical uses, and prostheses of the hand are being produced and proven to be functional. The advantages of three-dimensional prostheses are lower cost, customizability and rapid turnover. The major disadvantages are durability and initial set-up fees. Given that children can quickly outgrow an expensive prosthesis, the advantages of three-dimensional printed prostheses may outweigh the disadvantages. The feasibility of three-dimensional printing means that children are eligible to receive sophisticated devices earlier and more frequently than they would otherwise, given economic constraints.

Orthotics and prostheses both refer to external devices, though prostheses are more specifically meant to replace a missing part. One manner of considering low-functioning patients with cerebral palsy is that they are lacking useable parts, such as mobile fingers or opposable thumbs. The most common upper extremity contracture pattern in cerebral palsy patients is thumb in palm with clasped hand, followed by shoulder adduction and internal rotation, and wrist flexion with pronation. In spite of having contractures, even children with severe limitations maintain a small amount of active motion of either the wrist or elbow. This active motion in proximal joints can be used to motor distal motion by means of a prosthesis which is

driven by tenodesis. Templates for functional, three-dimensionally printed prostheses which give patients the ability to grasp and release by means of wrist or elbow motion are already available and have been utilized for pediatric patients with congenital finger amputations or malformations. Cerebral palsy patients with contracted, poorly mobile fingers and some small degree of control over wrist or elbow motion might also be eligible for utilizing such a device.

A systematic review and meta-analysis was recently performed on the use of orthotics, or splints, in children with cerebral palsy. Unlike constraint or bimanual therapies, orthotics can be applicable to lower-functioning patients. When looking only at functional, as opposed to non-functional, hand splints, preliminary data showed a small, immediate benefit. Some investigators likened functional hand splints to being utilized like spectacles for vision, with the improved use present only during wear, while others speculated that the gains made during usage would carry over into times without wear. Currently, insufficient data exists to determine which theory is most accurate.

**Study Design:** Prospective one group pretest-posttest design

Primary outcome measures: passive and active range of motion, MACS, Assisting Hand Assessment, Melbourne Assessment of Unilateral Upper Limb Function, Pediatric Motor Activity Log  
Secondary outcome measure: Pediatric Quality of Life Inventory

### **CHARACTERISTICS OF THE RESEARCH POPULATION**

**Number of Subjects:** Participants will be 12 children.

**Gender of Subjects:** Males and females will be enrolled

**Age of Subjects:** 4-17 years

**Racial and Ethnic Origins:** Participants of all racial and ethnic origins will be included.

**Inclusion Criteria:**

- Diagnosis: cerebral palsy
- 4-17 years old
- MACS levels III - V
- Active movement of wrist or elbow

**Exclusion Criteria:**

- MACS levels I, II
- Botox or orthopedic surgery in past 6 months
- Severe contractures
- Lack of voluntary arm motion

**Vulnerable Subjects:** Children are the target population. Appendix: Children will be uploaded. Some children may have cognitive limitations, so Appendix: Cognitively Impaired Subjects will be uploaded. A review of the patient's medical record as well as a discussion with parent/legal guardian will be used to assess the patient's ability to provide assent and sign the form. If unable to sign and patient is able to indicate and understanding of the study, verbal assent will be obtained. Additionally, children without the capacity to provide assent will be included because they may benefit from this study in that their upper extremity function might improve.

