All visits for this study are for research purposes. The patient will be scheduled for Visit 1, Screening Visit. At Visit 1, a pediatric occupational therapist will perform a comprehensive initial evaluation to determine functional level, range of passive and active upper extremity motion, presence of contractures, and level of spasticity/abnormal tone. The evaluation will include the following widely used measures of upper extremity function in patients with cerebral palsy: MACS, the Assisting Hand Assessment (AHA), Melbourne Assessment of Unilateral Upper Limb Function, and Pediatric Motor Activity Log (PMAL). From this information the occupational therapist will determine patient's eligibility for enrollment, i.e., if the patient meets inclusion and exclusion criteria. Additionally, for the patients that are enrolled in the study, this will serve as their initial evaluation.

Those patients determined to be eligible and signed consent/assent/authorization forms will be fitted with a three-dimensionally printed arm prosthesis, which uses wrist or elbow tenodesis for grasp and release. Three-dimensional printers can manufacture prostheses, which use proximal motion to activate opening and closing of the fingers.

Patients with MACS III have limited active finger and wrist motion. Many patients with MACS level IV have a small amount of active wrist motion and minimal finger motion. These two groups of patients can have prostheses with extension caps on the fingers and thumb driven by wrist motion. The palmar fingertips would then be utilized for sensory input and additional fine control. In contrast, those patients (some MACS IV and some MACS V) with unusable, contracted fingers and no wrist motion may need more involved prostheses. Similar to prostheses for children with congenital finger amputations, a prosthetic hand component would be fitted over the existing hand, and extension and flexion of the prosthetic fingers (not just caps) would be driven by elbow motion.

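### Does excluding severe contractures shut out the children for whom the elbow-driven prosthetic hand was designed?

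*Protocol*

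**What the plan says.** The Inclusion Criteria of the protocol admit children aged 4 to 17 with cerebral palsy, "MACS levels III - V" and "Active movement of wrist or elbow". The Exclusion Criteria then list "Severe contractures" and, as a separate item, "Lack of voluntary arm motion". Neither item is defined further, and no other section limits the contracture exclusion to particular joints or sets a grade for it.

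Methods and Procedures describes two devices. One puts caps on the child's own fingers and thumb and is driven by the wrist. It is meant for MACS III and for many children at MACS IV. The other is for a different group: "those patients (some MACS IV and some MACS V) with unusable, contracted fingers and no wrist motion may need more involved prostheses". For them "a prosthetic hand component would be fitted over the existing hand", and the elbow moves the prosthetic fingers. The fabrication steps in the same section cover both designs.

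The Background gives the rationale: "Cerebral palsy patients with contracted, poorly mobile fingers and some small degree of control over wrist or elbow motion might also be eligible" for such a device. It also states that "The most common upper extremity contracture pattern in cerebral palsy patients is thumb in palm with clasped hand".

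At Visit 1 an occupational therapist assesses passive and active range, contractures, and spasticity or tone, and decides eligibility from that evaluation. The planned sample is 12 children.

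**The concern.** A hand with unusable, contracted fingers sounds like a severely contracted hand. The Background counts a hand pattern among upper extremity contractures, so nothing in the text plainly puts the fingers outside the exclusion. A therapist who applied the criterion strictly could turn away a child for whom the second design exists.

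Two things would be at stake. First, the sample could drift towards the wrist-driven group, leaving few or no users of the elbow-driven hand, although the Background says that MACS IV and V have far fewer treatments available than higher levels. Second, if therapists read the term differently, eligibility would depend on who did the screening. With 12 children, a few such decisions would visibly change who is studied. An analysis plan could not repair this, because eligibility is settled before any data are analysed.

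**Working it through.** The protocol states no figure on this point, so there is nothing to recompute. The check is a reading of the eligibility lists against the device description.

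**1. A test case.** Take a child aged 4 to 17 with cerebral palsy, MACS V, fixed and unusable fingers, no active wrist movement and active elbow movement. The child meets every inclusion criterion, since "Active movement of wrist or elbow" is satisfied by the elbow alone. The child also fits the description of the second device's users. Exclusion then turns only on whether "Severe contractures" is taken to cover these fingers.

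**2. Does the protocol call these fingers severely contracted?** No. Methods and Procedures calls them contracted and unusable; the Background calls them contracted and poorly mobile. The step to severe is the reader's own clinical judgement.

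**3. Does the absence of wrist motion imply a wrist contracture?** Not on this text. The neighbouring sentences grade children by how much active wrist and finger movement they have, because that movement powers the device. The natural meaning is that there is no active wrist movement to use. Visit 1 assesses active range, passive range, contractures and tone as different things.

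**4. Are such children expected to enrol?** Yes. The fabrication text gives specific steps for subjects who will receive a full prosthetic hand. A reading of the exclusion that emptied that group would make those steps pointless.

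**5. Is there a reading under which everything fits?** There are two. The exclusion may concern the joints that drive the device, or it may refer to a degree of contracture beyond the one described for this group. The protocol states neither, but both are compatible with every section.

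**6. Does "Lack of voluntary arm motion" make the first of these readings redundant?** No. A child may have some voluntary arm movement and still have a fixed contracture that limits range or prevents a fit. The two items overlap in part and do different work.

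**7. How many children are affected?** This cannot be derived. The protocol gives no expected numbers by MACS level or by device. It refers to some children at MACS IV and some at MACS V for the elbow-driven hand, and it assigns many at MACS IV to the other design. Zero is an admissible value, and nothing in the protocol supports the claim that a large part of the MACS IV to V range is affected.

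**8. What happens to the analysis?** Data Analysis and Data Monitoring plans to compare each outcome at the initial evaluation, at the end of therapy and at 6 months, in one group. It plans no conclusion by MACS level or device. Each child is the child's own reference, so a stricter or looser screen changes who is described and leaves that comparison valid for the children enrolled.

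**The case for a change.** The best case for a change is that the text gives the therapist no basis for exempting the hand. The word contracture is used for a hand pattern in "The most common upper extremity contracture pattern in cerebral palsy patients is thumb in palm with clasped hand", the exclusion names no joint, and nobody has drawn the line between unusable, contracted fingers and a severe contracture. Clarifying the term would take one line and no new procedure, since contractures are already assessed at Visit 1.

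Much of this stands. The term is undefined, and a therapist could read it so as to exclude some children whom the device description has in mind. What does not stand is the further claim that the two sections cannot both be satisfied: steps 2 to 5 show that they can, and the document read as a whole favours a compatible reading. The Background sentence adds little, because it speaks of who might use such a device and not of who may enter this trial. The alternative remedy, dropping the elbow-driven design, would answer a contradiction that has not been shown.

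**Conclusion.** The concern does not call for a change to the plan. It comes down to an eligibility term left without a joint or degree, a gap that screening staff who know the device description would probably fill sensibly. The number of children affected among the 12 is unknown and may be zero.

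This conclusion rests on two assumptions. One is that the therapists who decide eligibility read the exclusion in the light of the two device designs, as the fabrication text implies. The other is that the results describe the children actually enrolled, including their MACS levels and devices, so that a reader can see whom the findings cover. If a screening therapist did apply the strict reading, the loss would be in how widely the findings apply to the lowest-functioning children. The comparison over time within each child would still hold.

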### **METHODS AND PROCEDURES**

#### **Methods and Procedures**

Participants will be 12 children, aged 4-17 years, with cerebral palsy and MACS level III - V

All patients, with CP and upper extremity involvement, who are being seen during a regularly scheduled clinic/office/occupational therapy visit by the PI, co-investigator or occupational therapist, and are potentially eligible for enrollment in the study will be provided information about the study. The PI, co-investigator, occupational therapist or research coordinator will explain the project to the child and the child's parents. The parents will be asked if they are interested in having their child voluntarily participate in the study. The Consent form (please see Process of Consent section below for further details) will be presented to the parent/legal guardian and the age appropriate Assent form will be presented to the child. If parent/legal guardian and child agree to participate, then they will be asked to sign the Consent and Assent forms.

Additionally, the PI, co-investigator and occupational therapists will review their own individual databases for potential subjects and contact their own patients by phone to describe the research project. The Telephone Recruitment Script and Waiver of Authorization have been uploaded. If patient and parent are interested, then patient will be referred to the occupational therapist. For these subjects, the occupational therapist or research coordinator will be obtaining consent/assent (please see Process of Consent section below for further details) when the patient comes for Visit 1.

All visits for this study are for research purposes. The patient will be scheduled for Visit 1, Screening Visit. At Visit 1, a pediatric occupational therapist will perform a comprehensive initial evaluation to determine functional level, range of passive and active upper extremity motion, presence of contractures, and level of spasticity/abnormal tone. The evaluation will include the following widely used measures of upper extremity function in patients with cerebral palsy: MACS, the Assisting Hand Assessment (AHA), Melbourne Assessment of Unilateral Upper Limb Function, and Pediatric Motor Activity Log (PMAL). From this information the occupational therapist will determine patient's eligibility for enrollment, i.e., if the patient meets inclusion and exclusion criteria. Additionally, for the patients that are enrolled in the study, this will serve as their initial evaluation.

Those patients determined to be eligible and signed consent/assent/authorization forms will be fitted with a three-dimensionally printed arm prosthesis, which uses wrist or elbow tenodesis for grasp and release. Three-dimensional printers can manufacture prostheses, which use proximal motion to activate opening and closing of the fingers.

Patients with MACS III have limited active finger and wrist motion. Many patients with MACS level IV have a small amount of active wrist motion and minimal finger motion. These two groups of patients can have prostheses with extension caps on the fingers and thumb driven by wrist motion. The palmar fingertips would then be utilized for sensory input and additional fine control. In contrast, those patients (some MACS IV and some MACS V) with unusable, contracted fingers and no wrist motion may need more involved prostheses. Similar to prostheses for children with congenital finger amputations, a prosthetic hand component would be fitted over the existing hand, and extension and flexion of the prosthetic fingers (not just caps) would be driven by elbow motion.

The fabrication of the prosthesis will involve several steps. First the measurements by the occupational therapist will include: (1) circumferential measurements of all fingers, thumb, web space, wrist and forearm, and (2) length measurements from (a) elbow to wrist, (b) wrist to each metacarpal joint, (c) each metacarpal joint to proximal interphalangeal joint, (d) each proximal interphalangeal joint to distal interphalangeal joint, (e) each distal interphalangeal joint to finger tip, (f) metacarpal to interphalangeal joint of thumb, and (g) interphalangeal joint to tip of thumb. These measurements will be inputted to the software in the computer connected to the 3D printer. This software drives the printer to produce the following prosthetic components for the subjects who will be using their own fingers: (1) 3 dorsal caps per finger, which fit between the joints and the distal joint and tip, (2) 2 dorsal caps for the thumb, which fit between the joints and the joint and tip, (3) dorsal hand hood, which fits between wrist and metacarpals, and (4) dorsal forearm hood. For the subjects for whom a prosthetic hand is being fabricated, the same measurements will be used to make the prosthetic components with the same components being made for the dorsum of the forearm and hand, but complete replicas of the fingers and thumb will be made. For both designs, all of these components are interconnected with nylon cord and tensioning fasteners. The fasteners are used to adjust the tension to provide the movement at the joints of the prosthesis that is generated by either the subject's own active elbow flexion, or wrist flexion or extension. All of the components will be made from a cornstarch-based material called polylactic acid. According to FDA regulations, external prosthetic components are exempt. As SOC, children have previously received similar splints of both designs, but fabricated manually by an occupational therapist.

After the prosthesis has been fabricated, the occupational therapist will place it on the patient's arm and hand. The therapist will assess the fit of all of the components and ask patient if there are any areas of discomfort. Therapist will adjust prosthesis to eliminate any areas of discomfort. Additionally, the therapist

will evaluate the ease of movement between all of the components and adjust the tension of the cords as needed.

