#### **Data Analysis and Data Monitoring**

Demographics will be reported. Passive and active range of motion measurements and the MACS, AHA, Melbourne Assessment, PMAL and the PedsQL scores at initial evaluation, end of occupational therapy treatment and 6 months follow-up will be compared. DSMP has been uploaded.

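### Should MACS cease to be a primary outcome because the Visit 1 rating is also the entry filter and the baseline?

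*Protocol*

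**What the plan says.** The Study Design paragraph describes a "Prospective one group pretest-posttest design" and opens its outcome list with "Primary outcome measures: passive and active range of motion, MACS", followed by the Assisting Hand Assessment (AHA), the Melbourne Assessment and the Pediatric Motor Activity Log (PMAL). On sample size: "Participants will be 12 children".

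The Inclusion Criteria require "MACS levels III - V", and the Exclusion Criteria rule out "MACS levels I, II". Under Methods and Procedures, Visit 1 covers MACS and the other function measures. It then says: "From this information the occupational therapist will determine patient's eligibility for enrollment". For enrolled children, "this will serve as their initial evaluation". Data Analysis and Data Monitoring plans that the scores "at initial evaluation, end of occupational therapy treatment and 6 months follow-up will be compared". It names no test, significance level or power.

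Two further places matter. Method of Subject Identification and Recruitment describes candidates as already at MACS III to V, and picked out at an ordinary visit, before Visit 1 is booked. The Visit Schedule has every assessment at Visits 13 and 14 done both with and without the prosthesis.

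**The concern.** Two things look wrong.

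**Selection on the baseline.** The rating that admits the child is also the rating from which change is measured. Some children enter only because Visit 1 placed them one level too low in ability. When they are rated again at their true level, they appear to have improved. Their opposites, true level III children rated II at Visit 1, were turned away and cannot offset them. Without a control group, such a III-to-II move cannot be told apart from a treatment gain.

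**Coarseness.** MACS has five levels, so change registers only in whole levels. With 12 children, only a large shift could reach significance.

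If either effect were large, a primary outcome could mislead: by false improvement in the first case, by missing a real benefit in the second. The suggested remedy was to remove MACS from the primary outcomes and report it descriptively.

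**Working it through.** The protocol gives no calculation to reproduce, so the check sizes each effect under stated assumptions.

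**1. Inputs**
- From the protocol: n = 12; entry at III to V; levels IV and V make up 15-30% of children with cerebral palsy (Background).
- Assumed: the true level is fixed and ratings are independent. Each rating is one level too high with probability e and one too low with probability e (no error beyond I or V). So e = 5% means a mid-scale child is misrated 10% of the time in total.
- Assumed mixes for I/II/III/IV/V: A = 20/20/20/20/20; B = 25/25/20/17/13 (30% at IV-V); C = 35/30/20/9/6 (15% at IV-V).

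**2. Net false gain**

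Given the true level, two ratings are exchangeable, so moves up and down within III to V cancel. What remains is the share rated III to V at Visit 1 and I or II later, almost all of it III-to-II. The chance of being rated III to V is 0, e, 1−e, 1 and 1 for true levels I to V. Writing π for the mix:

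- Visit 1 the only filter: net = e(1−e)(π_II + π_III) / [π_II·e + π_III(1−e) + π_IV + π_V]
- One earlier independent rating also at III to V: net = e(1−e)[π_II·e + π_III(1−e)] / [π_II·e² + π_III(1−e)² + π_IV + π_V]

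Example, mix A, e = 0.05:
- Unscreened: 0.0475 × 0.40 / 0.600 = 0.0317; × 12 = 0.38 children.
- Screened: 0.0475 × 0.20 / 0.581 = 0.0164; × 12 = 0.20 children.

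Example, mix C, e = 0.10:
- Unscreened: 0.09 × 0.50 / 0.360 = 0.125; × 12 = 1.50.
- Screened: 0.09 × 0.21 / 0.315 = 0.060; × 12 = 0.72.

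| Net false gain, of 12 | Mix A | Mix B | Mix C |
|---|---|---|---|
| e = 5%, screened | 0.20 | 0.24 | 0.35 |
| e = 5%, Visit 1 only | 0.38 | 0.51 | 0.80 |
| e = 10%, screened | 0.38 | 0.48 | 0.72 |
| e = 10%, Visit 1 only | 0.72 | 0.96 | 1.50 |

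At e = 2.5% with screening, the range is 0.10 to 0.17.

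**3. Could the lean alone give a significant result?**

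Assume an exact two-sided sign test at 0.05. Sum the trinomial probabilities of every split of 12 children into better, worse and unchanged for which improvement is significant.

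- Screened: 0.01-0.02% of trials at e = 5%; 0.2-0.4% at e = 10%. The largest case, mix C, has P(up) = 0.171 and P(down) = 0.111, giving 0.40%.
- Visit 1 only: 0.03-0.12% at e = 5%; 0.4-1.6% at e = 10%. The largest case has P(up) = 0.227 and P(down) = 0.102, giving 1.6%.

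All are below the 2.5% that such a test nominally allows in that direction.

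**4. Coarseness**

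Same sign test:
- 6 better, 0 worse: 2 × 0.5⁶ = 0.031. With 5 and 0: 2 × 0.5⁵ = 0.0625.
- 8 better, 1 worse: 0.039. With 7 and 1: 0.070.
- If 40%, 50% or 60% truly gain a level and none worsens, P(at least 6 of 12 gain) is 33%, 61% or 84%.

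None of these figures uses the entry rule or the choice of baseline. They would be the same if a separate rating served as baseline.

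**The case for a change.** The strongest case for a change is that the outcome list, the entry rule and the baseline visit are all fixed in the protocol, so no analysis plan can undo the selection. The direction of the lean does not depend on the assumed error rate or mix, as long as ratings at the two visits share the same error pattern. A III-to-II move is therefore ambiguous. The remedy costs only wording, since MACS would still be collected and range of motion, AHA, Melbourne and PMAL would stay primary.

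The direction and the ambiguity stand. So does a caution about the screened figures: they treat the earlier clinic impression as an independent rating. If it repeats the same error as Visit 1, the size moves towards the unscreened rows.

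The rest does not carry the remedy. Demoting MACS changes no collected value, does not make the other measures more precise, and leaves the same ambiguity in the same table. The lack of a control affects every comparison with Visit 1, not only MACS. A repeat MACS at the existing Visit 2, used as baseline, would meet the selection point more directly. But it adds an assessment to remove a shift that is under one child in all but the most pessimistic setting. A table of levels by visit and prosthesis condition, with III-to-II moves read cautiously, is ordinary reporting and needs no amendment.

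**Conclusion.** The concern is right about the mechanism but does not justify a change. The lean in the Visit 1 comparison is about 0.20 to 0.35 of 12 children at e = 5% and 0.38 to 0.72 at e = 10%, given the recruitment screen. The extreme without that screen is 1.50. It would rarely produce a significant result, and it does not touch the on-versus-off contrast made within Visits 13 and 14.

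These sizes rest on error rates, level mixes and a sign test that the protocol does not state. The direction rests only on equal error patterns at the two visits.

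The low chance of showing a modest MACS change belongs to a one-group study of 12 children on a five-level scale. The protocol claims no power that this would contradict. Whether MACS ranks as primary or descriptive is a fair trade-off for the investigators, and demoting it would gain nothing in the data or in the other measures.
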